5.5.2. Examination of Subgroups

The list of subgroups may be used in descriptive summaries and statistical analyses. Additional subgroups of clinical interest may also be considered for post-hoc analyses.

- If the percentage of subjects responding is small within a subgroup, then the subgroup categories may be refined prior to unblinding the trial.
- If the category cannot be refined further, then descriptive rather than statistical comparisons may be performed for the subgroup.

| Subgroup | Categories |
|------------------------------------|--|
| Age Group | <65 vs. ≥65 If there are less than 10 subjects ≥65, this sub group will be summarised but not analysed |
| Race | Black vs. Non-Black |
| Gender | Female vs Male |
| Country Region | USA/Canada: USA and Canada, Europe: France, Germany, Netherlands, Spain Rest of World: All other countries |
| Baseline SLEDAI | ≤9 vs. ≥10 |
| Baseline Immunosuppressant Use | Use vs. Non-use |
| Baseline corticosteroid dose | ≤10 mg/day vs. >10 mg/day (Prednisone equivalent) |
| Baseline complement level | At least one low C3/C4 vs. No low C3/C4 |
| Baseline anti-dsDNA | ≥30 IU/mL vs. <30 IU/mL |
| Baseline C3/C4 levels & anti-dsDNA | At least one low C3/C4 & anti-dsDNA ≥30 IU/mL vs. Not (At least one low C3/C4 & anti-dsDNA ≥ 30 IU/mL) |
| Baseline BLYS (free) Protein | ≥ 75 th Percentile vs. < 75 th Percentile |
| Baseline RNA Interferon Signature | Low vs. High |

5.6. Multiple Comparisons and Multiplicity

[figure not shown]
The primary comparison of interest is the comparison between Arm B (combination) vs Arm A (control) for the primary endpoint (SLEDAI-2K ≤ 2 (IBA)) in the MITT population. This analysis will be adjusted for baseline SLEDAI-2K (≤9 vs. ≥10), baseline immunosuppressant (Use vs. Non-use) and baseline corticosteroid dose (≤10 mg/day vs. >10 mg/day).

For the analysis of the primary and the major secondary efficacy endpoints, a step-down sequential testing procedure will be used to control the overall type 1 error rate for comparing Arm B (combination) vs Arm A (control). With this procedure, the primary endpoint and the two major secondary endpoints will be evaluated for statistical significance based on a pre-specified sequence for interpretation (i.e. the endpoints based on SLEDAI-2K score (IBA) ≤ 2 at Week 52, followed by Clinical SLEDAI-2K score (IBA) = 0 at Week 64 and then SLEDAI-2K score (IBA) ≤ 2 at Week 104, see [Figure 1](#)). Specifically, endpoints will be tested in the sequence above (2-sided alpha=0.05)

provided that statistical significance is achieved by all prior tests. If at any point in the sequence statistical significance is not met, then subsequent endpoints in the sequence cannot be deemed statistically significant. The primary endpoint will be tested at the primary analysis using the first locked database; the first and second major secondary endpoints will be tested using the end of study locked database.

An overview of the multiplicity control is provided in [Figure 1](#).

Figure 1 Overview of Multiplicity Control

Analyses of other efficacy endpoints will not be subject to any multiplicity adjustment.

5.7. Cut-off Date for Primary Analyses (Year 1)

For study participants continuing in the study past the Week 52 visit, the cut-off date in the Year 1 analysis dataset will be the date of the Week 52 visit.

For participants who discontinue from the study prior to the Week 52 visit, the exit/withdrawal visit will be assigned to an assessment window as defined in [Section 15.3](#). Exit/withdrawal visit assigned to week 52 or earlier will be included in the week 52 report; exit/withdrawal visits assigned to an assessment window from Week 60 or later, will be reported in the Week 104 analysis.

Participants who withdraw at or prior to the Week 52 visit will have their follow-up visit included in the Year 1 reporting if the follow-up visit is prior to or on the day of the last subject's Week 52 visit. Follow-up visits that occur after the last subjects' Week 52

assessment will be reported in the Year 2 reporting. Hence subjects who withdraw at or prior to Week 52 will have a cut-off date that is the earliest of their week follow-up date and the last subject's Week 52 date.

Displays for the primary analysis reporting effort will include all data collected up to and including the Year 1 cut-off date for each participant. This includes adverse events and concomitant medications with a start date less than or equal to the cut-off date.

5.8. Database for End of Study Analyses (Year 2 and Years 1&2 Combined)

The final database will be an accumulation of all data from both Year 1 and Year 2 including the 8-week Follow-up visit.

5.9. Study Withdrawal

Study withdrawal (referred to in the protocol as dropout), is the combination of subjects who withdraw, are lost to follow-up (LTFU), or die during the study

Study withdrawal is defined as any subject who withdraws from the study prior to the analysis visit of interest (e.g. Week 52, Week 64, Week 104) and does not have a visit within ± 28 days of the target analysis visit date (excluding follow up visits).

This rule is applied consistently across all efficacy endpoints. The assessment of whether or not a subject had a visit within the ± 28 day of an analysis visit (e.g. Week 52) is performed at the domain level [e.g., a subject who had visit within 28 days for SLEDAI-2K but not a SLICC ACR assessment would be assessed on their observed data for SLEDAI-2K but would be considered withdrawn (non-responder) in SLICC ACR assessment].

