9.6. Efficacy Assessments

Overview

Planned time points for all efficacy assessments are listed in the SoA (Section 2). At selected time points, the SLEDAI-2K is performed by independent assessors who are blinded with regard to the treatment group assignment. Time windows are provided for each study visit to allow flexibility in site and participant scheduling. All study visits should occur within the visit window of the scheduled study visit. Details regarding the conduct of the efficacy assessments described below are provided in the SRM. In addition, information from the SLEDAI-2K, PGA, laboratory tests, use and doses of SLE medications, and clinical evaluations will be used to calculate the Lupus Low Disease Activity State (LLDAS) [Franklyn, 2016].

SLEDAI-2K

The SLEDAI-2K is a clinical index for measuring SLE disease activity in the previous 10 days.

Physician's Global Assessment

The Physician's Global Assessment (PGA) is a physician-reported visual analogue scale that provides an overall measure of the participant's current disease activity.

SLICC-ACR Damage Index

The Systemic Lupus International Collaborating clinics (SLICC) -American College of Rheumatology (ACR) Damage Index measures irreversible changes occurring since the diagnosis of SLE.

SLE Flare Index

The SLE Flare Index identifies whether a participant has experienced a mild/moderate or severe flare.

Lupus Low Disease Activity State

The Lupus Low Disease Activity State (LLDAS) incorporates multiple measures of disease activity, specifically:

- SLEDAI-2K ≤4, with no activity in major organ systems (renal, CNS, cardiopulmonary, vasculitis, fever) and no hemolytic anemia or gastrointestinal activity
- No new features of lupus disease activity compared with the previous assessment
- PGA (scale 0-3) ≤ 1
- Current prednisolone (or equivalent) dose ≤ 7.5 mg daily
- Well tolerated standard maintenance doses of immunosuppressive drugs and approved biological agents, excluding investigational drugs.

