| 22.29. | 22.28 | MITT | SLEDAI-2K (PI) - Organ System Worsening by Organ System and Visit Among Subjects with No Organ System Involvement at Baseline [1] (Observed) (Year 1&2) | |
| Physician Global Assessment (PGA) | | | | |
| 22.30. | 22.29 | MITT | Physician Global Assessment (PGA) - Change from Baseline by Visit (Hypothetical) (Year 1&2) | |
| Systemic Lupus International Collaborating Clinics (SLICC) | | | | |
| 22.31. | 22.30 | MITT | SLICC/ACR Damage Index Worsening (Change>0) Compared with Baseline at Week 104 (Treatment Policy, WOCF) | |
| Lupus Low Disease Activity State (LLDAS) | | | | |
| 22.32. | 22.31 | MITT | Lupus Low Disease Activity State (LLDAS) (PI) by Visit (Treatment Policy) (Year 1&2) | |
| 22.33. | 22.32 | MITT | Lupus Low Disease Activity State (LLDAS) (PI) and its Components at Weeks 52, 64 and 104 (Treatment Policy) (Year 1&2) | |
| Modified Disease Control | | | | |
| 22.34. | 22.39 | MITT | SLEDAI-2K Score <=2 (IBA), Without Current Immunosuppressants, Without Current Belimumab dosing (Arms A & B) and Corticosteroids dose <=5mg/day at Week 104 (COVID-19 Modified, Treatment Policy) | |
| Proteinuria | | | | |
| 22.35. | NEW | ITT | Proteinuria Shifts from Baseline by Visit (Observed) (Year 1&2) | 
 • New output (of interest following post SAC request for Year 1) |

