| | 
 • Time to clinical remission sustained to Week 104 , defined as Clinical SLEDAI-2K score (PI) =0 (Section 15.6.3), achieved without immunosuppressants and with corticosteroids at a prednisone equivalent dose of 0 mg/day. • Duration of disease control, defined as SLEDAI-2K score (PI) ≤2, achieved without immunosuppressants and with corticosteroids at a prednisone equivalent dose of ≤5 mg/day • Duration of clinical remission, defined as Clinical SLEDAI-2K score (PI) =0 (Section 15.6.3), achieved without immunosuppressants and with corticosteroids at a prednisone equivalent dose of 0 mg/day. • Change from baseline in SLEDAI-2K score (PI) by visit • Proportion of participants with SLEDAI-2K (PI) organ improvement by visit • Proportion of participants with SLEDAI-2K (PI) organ worsening by visit • Change from baseline in Physician Global Assessment (PGA) by visit • Proportion of participants with any SLICC Damage Index worsening (change >0) compared with baseline at Week 52 and Week 104 • Proportion of participants that meet the Lupus Low Disease Activity State (LLDAS) response criteria by visit. The LLDAS incorporates multiple measures of disease activity, specifically: (1) SLEDAI-2K ≤4, with no activity in major organ systems (renal, CNS, cardiopulmonary, vasculitis, fever) and no hemolytic anaemia or gastrointestinal activity; (2) no new features of lupus disease activity compared with the previous assessment; (3) PGA (scale 0-3) ≤1; (4) current prednisolone (or equivalent) dose ≤7.5 mg daily; and (5) well tolerated standard maintenance doses of immunosuppressive drugs and approved biological agents, excluding investigational drugs. • Proportion of participants with a state of disease control, defined as a SLEDAI-2K score (PI) ≤2, achieved without immunosuppressants and with corticosteroids at a prednisone equivalent dose of ≤5 mg/day, by visit; using the principal investigators assessment of SLEDAI-2K • Proportion of participants with a state of clinical remission, defined as a Clinical SLEDAI-2K score (PI) =0 (Section 15.6.3), achieved without immunosuppressants and with corticosteroids at a prednisone equivalent dose |

| Objectives | Endpoints |
|--|---|
| | of 0 mg/day, by visit; using the principal investigators assessment of SLEDAI-2K. |
| Secondary (Safety) Objectives | Secondary (Safety) Endpoints |

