Assessments after IP discontinuation and assessments after Treatment Failure will be included. Subjects who withdraw from the study will be non-responders.

The impact of the different IP discontinuation components of the endpoint for the Hybrid and composite estimands is summarised by considering 6 hypothetical scenarios:

Table 2 Scenarios for the components of the Hybrid and composite endpoint

| Example Subject | SLEDAI-2K score at Week 52 | Study Withdrawal(including Lost to Follow-up, or Death) prior to Week 52 | Treatment Failure prior to Week 52 | IP Discontinuation prior to Week 52 | Main Estimand Hybrid | Supplemental Estimand Composite |
|-----------------|--|--|------------------------------------|-------------------------------------|----------------------|---------------------------------|
| 1 | >2 | N | N or Y | N or Y | NR | NR |
| 2 | <=2 | N | N | N | R | R |
| 3 | <=2 | N | N | Y | R | NR |
| 4 | <=2 | N | Y | N or Y | NR | NR |
| 5 | Incomplete* or entirely missing | N | N or Y | N or Y | NR | NR |
| 6 | Missing - does not exist due to study withdrawal | Y | N or Y | Y | NR | NR |

R = Responder; NR = Non-Responder

*Incomplete: does not include partial scores where it is possible to determine that the total score must be >2, or that the maximum possible score (assuming worst case for missing data) is <=2 (see Section 15.6.4 Partial but informative SLEDAI-2K score).

A full breakdown of scenarios ‘by subject type’ and including Hybrid On Treatment and Treatment Policy is provided in Section 15.6.4

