7.6.3. Strategy for Intercurrent (Post-Randomization) Events

Treatment failure and study withdrawal will not be considered as components of the endpoint and an observed case analysis will be conducted.

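### SAP 5.9 uses SLICC damage as its example of withdrawn = non-responder, contradicting the observed-case rule in 7.6, and never says what non-responder means for a worsening endpoint

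*SAP*

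**What the plan says.** The endpoint, listed among the other (non-major) secondary efficacy endpoints in SAP 2.2, is "Proportion of participants with any SLICC Damage Index worsening (change >0) compared with baseline at Week 52 and Week 104". Protocol 9.6 says the index "measures irreversible changes occurring since the diagnosis of SLE". The event being counted is therefore a harm.

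Three places in the SAP bear on participants who leave the study:

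- **Section 5.9, Study Withdrawal.** Withdrawal "is the combination of subjects who withdraw, are lost to follow-up (LTFU), or die during the study". It applies when a participant leaves before the analysis visit and has no visit within 28 days of the target date. The section adds: "This rule is applied consistently across all efficacy endpoints". It then says the 28-day check is made separately for each assessment domain. In its example, someone with a SLEDAI-2K in the window but no SLICC keeps the observed SLEDAI-2K result but "would be considered withdrawn (non-responder) in SLICC ACR assessment".
- **Sections 7.6.3 and 7.6.5, observed-case proportion endpoints.** This is where the SLICC analysis is specified. "Treatment failure and study withdrawal will not be considered as components of the endpoint", and the analysis is observed case. The SLICC entry adds that carrying the worst score forward corrects scores at attended visits and does not fill in missed ones. Results are tabulated as the percentage of subjects with a response.
- **End-of-study addendum, Section 2.1.4, Table 22.31.** The title reads "SLICC/ACR Damage Index Worsening (Change>0) Compared with Baseline at Week 104 (Treatment Policy, WOCF" (closing bracket omitted). SAP 7.1.4, describing the Treatment Policy strategy for the primary endpoint, says: "Subjects who withdraw from the study will be non-responders".

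**The concern.** A programmer following 5.9 keeps withdrawn participants in the SLICC denominator. One following 7.6 drops them. Section 5.9 cannot be dismissed as a general default that never considered this endpoint, because SLICC is the case it names.

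The term non-responder also has no stated meaning here. For disease control or remission, the non-responder category is the bad outcome, so assigning dropouts to it is conservative. For SLICC, the modelled outcome is worsening and 7.6.5 tabulates it as the response. A non-responder is then someone without new damage, and the same rule becomes favourable to participants who withdrew, were lost or died. On an index of irreversible damage that would understate harm, more so in the arm with more withdrawal.

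**Working it through.** **Reading the passages together**

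| Source | Withdrawn participant with no SLICC in the window | Denominator |
|---|---|---|
| SAP 5.9 example | non-responder | all participants |
| SAP 7.6.3 and 7.6.5 | not analysed | assessed participants only |
| Table 22.31 title, read through 7.1.4 | non-responder | all participants |

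No section defines non-responder for SLICC, so the 5.9 row has two possible codings: no worsening (literal) or worsened.

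**Inputs**

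- Arm sizes 70 (A) and 140 (B): Protocol 10.2 targets.
- Withdrawal 10% to 15%: the only dropout figure available, from the Amendment 02 rationale in Protocol Appendix 13. It is an overall figure; splitting it as 10% in A and 15% in B is an assumption.
- Worsening rate r among assessed participants: not in the documents. Assumed equal in both arms and varied over 3%, 5% and 10%.

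The plan states no SLICC rate, power or sample size, so there is no figure of its own to reproduce.

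**Formulas**, with d the share withdrawn:

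- observed case: r
- withdrawn = no worsening: r(1 − d)
- withdrawn = worsened: r(1 − d) + d

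**Worked case, r = 5%**

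- Assessed: A 70 × 0.90 = 63; B 140 × 0.85 = 119.
- Expected events among them: A 63 × 0.05 = 3.15; B 119 × 0.05 = 5.95.
- Observed case: 3.15/63 = 5.0% and 5.95/119 = 5.0%. Odds ratio B versus A = 1.00.
- Withdrawn = no worsening: 3.15/70 = 4.5% and 5.95/140 = 4.25%. Odds ratio = (0.0425/0.9575)/(0.045/0.955) = 0.94.
- Withdrawn = worsened: (3.15 + 7)/70 = 14.5% and (5.95 + 21)/140 = 19.25%. Odds ratio = (0.1925/0.8075)/(0.145/0.855) = 1.41.

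**Range over r** (A 10%, B 15% withdrawn)

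| r | Observed case | Withdrawn = no worsening | Withdrawn = worsened |
|---|---|---|---|
| 3% | 1.00 | 0.94 | 1.46 |
| 5% | 1.00 | 0.94 | 1.41 |
| 10% | 1.00 | 0.94 | 1.31 |

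Swapping the withdrawal rates (A 15%, B 10%) gives 1.06 to 1.07 and 0.68 to 0.76 for the last two columns. With equal withdrawal in both arms, all three rules give an odds ratio of 1.00, but the literal 5.9 rule still lowers each arm's damage rate by a relative 10% to 15%.

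These are unadjusted odds ratios; the plan's model is covariate-adjusted. They compare coding rules and do not estimate the true effect, since damage in withdrawn participants is unobserved.

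**The case against.** The best defence is that 7.6 is specific and clear, and that a detailed endpoint specification would normally prevail over an illustration in a definitions section. The sentence in 5.9 about consistency can also be read as covering only who counts as withdrawn. It cannot mean withdrawn = non-responder everywhere, because 7.7.5 censors withdrawals for flare and 7.9 imputes after withdrawal for continuous endpoints. This narrows the problem to the SLICC example, but the example remains and names the endpoint.

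A reader might infer that the addendum, as the later text, replaces the observed-case rule with the non-responder rule. The documents do not support that:

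- The column recording major modifications is blank for Table 22.31.
- Flare tables in the same addendum carry the Treatment Policy label although 7.7.5 censors withdrawals.
- SAP 7.11 attaches treatment policy and observed together to the organ endpoints.
- For SLICC, the label fits the 7.6.5 statement that data count regardless of treatment failure or discontinuation of study drug.
- The definition in 7.1.4 is written for the primary endpoint.

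The title is therefore ambiguous, not a change of rule.

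A reader might also infer that the plan settles on crediting dropouts with no damage. That is only the literal reading of 5.9; the direction is never written down.

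Finally, SLICC is scheduled at the Early Withdrawal visit, so some participants who leave will have a usable value if that visit falls in the window. This reduces the number affected without removing the conflict.

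**Conclusion.** The conflict between 5.9 and 7.6 is explicit and should be removed. Taken literally, 5.9 would count withdrawn, lost and deceased participants as free of new damage. The reverse coding is also possible, because the SAP does not exclude it, and it would distort the result by more.

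Under the assumptions above (worsening of 3% to 10% and equal in both arms, withdrawal of 10% versus 15%), the odds ratio moves from 1.00 to about 0.94 under one coding and to about 1.3 to 1.5 under the other. The worsening rates and the split of withdrawal between arms are assumed, so these figures show sensitivity to the rule and do not predict the trial's result. A claim that the plan favours a particular arm would go beyond the documents.

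The consequence is limited. SLICC worsening is a non-major secondary endpoint outside the step-down testing sequence, and no primary or major secondary conclusion depends on it. It does still receive an odds ratio and a p-value.

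**What to change.** Three edits to the text:

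1. Delete the SLICC illustration from SAP 5.9, or replace it with an endpoint for which withdrawn = non-responder is intended.
2. State in 5.9 that the withdrawn = non-responder rule does not apply to the observed-case endpoints in 7.6.
3. Retitle Table 22.31 to match 7.6, for example Observed, WOCF.

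If a withdrawal component for SLICC is wanted after all, as a sensitivity analysis for instance, the text must say whether withdrawn participants and deaths are coded as worsened or not worsened.

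The cost is two wording changes and one table title. No new data are needed, and the analysis specified in 7.6 is unchanged.

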5.10. Treatment Failures

Treatment failures are subjects meeting any of the criteria defined below, from the time they 1st met the criteria:

- Received a protocol prohibited medication
- Arm A&B: Received immunosuppressants after Week 4 rituximab infusion visit;
Arm C: Increased immunosuppressants (at a dose higher than at baseline and Week 12) after Week 12
- Arms A&B only: Received PI prescribed re-start belimumab medication after Week 52 visit and prior to Week 104 visit
- Started any new immunosuppressant after Day 1
- Received a prednisone equivalent corticosteroid 7-day average dose of >5 mg/day after Week 26 visit
- Received a dose above the allowable level or after a protocol specified timepoint (Section 7.7.1 of the protocol) prior to Week 52 visit

Further detail is provided in Section 15.6.15 Treatment Failure Rules During Study Conduct

5.11. On Study

For Year 1, on study is defined as from 1st dose of belimumab to the earliest of:

- Week 52 visit assessment
- Study withdrawal (including LTFU and Death)

However, for subjects that withdraw during Year 1, the on treatment period could end later than the on study period. In this situation the on study period will be reset such that it ends at the same time as the on treatment period.

NOTE: Some subjects who are enrolled toward the end of the enrolment period and withdraw at or near their Week 52 assessment may have some of their Year 1 on study period reported at the end of the study (Section 5.7).

For Year 2, on study is defined as from the Week 52 visit assessment* until the date of study completion or study withdrawal (including LTFU and death).

*Subjects who did not complete week 52 but had not withdrawn prior to Week 52, and have post Week 52 assessments will use scheduled visit date.

For Year 1&2 on study is defined as from the 1st dose of belimumab until the date of study completion or study withdrawal (including LTFU and death).

5.12. On Treatment

For Year 1 on treatment is defined as from 1st dose of belimumab to the latter of: last dose of belimumab + 28 days or last dose of rituximab + 28 days

For Year 1&2 arm C, on treatment is defined as from 1st dose to last dose of belimumab + 28 days.

For Year 2 Arms A&B on treatment is not defined as there is no on treatment reporting (as all subjects are off treatment)

5.13. Race Hierarchy (minority rule)

If multiple race categories are checked on the eCRF, the subject will be assigned to a unique race group based on which of the races checked appears first in the list below:

1. Native Hawaiian or Other Pacific Islander
2. American Indian or Alaska Native
3. Asian
4. African American/African Heritage
5. White

For example, if African American/African Heritage and Asian are both checked, then the subject will be assigned as Asian since it appears highest in the list. Race assigned based on this minority rule will be applied to all analyses related to race (as per PSAP). In the race and racial combination details table, subjects with multiple race categories checked will be reported in the race per the minority rule as well as in the multiracial category.

